#### **REPORTING TO EC/CA**

Depending on the local requirements or following agreement between both parties, the sponsor or the principal investigator will be responsible for performing safety reporting to the Ethics Committee according to the relevant local regulatory requirements.

The sponsor will be responsible for reporting to the National Competent Authority according to national requirements and in line with MEDDEV 2.7/4 and/or MEDDEV 2.12-1, as applicable.

## **IX. INVESTIGATIONAL DEVICES DISTRIBUTION AND ACCOUNTABILITY**

The PI is responsible for ensuring that the investigational devices are used only under the PI’s supervision and are only used according to this protocol and any approved amendments. At the time of each study, Harpoon will provide the proper quantity of investigational devices the persons authorized to participate in the study. Harpoon will maintain adequate records of the receipt and disposition of all investigational devices. Harpoon and/or MedPass shall document in CRFs the lot numbers of the devices used during a case. Unused devices will be taken back by Harpoon Medical upon completion of a patient. No devices will be left at the study site.

## **X. STATISTICAL ANALYSIS**

This is an early feasibility study. The sample size for this study was determined from the first early feasibility study for this device for the treatment of mitral regurgitation at the conclusion of the procedure and at the time of the hospital dismissal and at one year. Specifically the percentage of patients that demonstrate MR reduction from severe to </+ moderate at the conclusion of the procedure and at 30 days. These data will be used to assess the safety and performance of the device when used on a human patient. These data will be used to assess initial safety and performance of the Harpoon Medical Device, and are not designed to test a statistical hypothesis, therefore a formal sample size has not been calculated. All data will be captured on an intent-to-treat basis. Data will be reported as descriptive statistics.

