## II. STUDY SUMMARY

Title:	Safety and Performance study of the Harpoon Medical Device in patients with degenerative mitral regurgitation
Protocol Number:	HMEFS-2000 Ver 00a
Design:	This is a prospective, single arm, nonrandomized, early feasibility study to evaluate the safety and performance of the Harpoon Medical Device.
Study Duration:	Projected enrollment of first patient December 2016 Projected exit of final patient: December 2019
Primary Objective:	The primary objective of this study is to evaluate the safety and performance of the Harpoon Medical Device.
Patient Population:	Patients with “Severe” mitral regurgitation as a result of posterior, bi-leaflet or anterior prolapse.
Sample Size:	Up to twenty (20) patients in PL will be enrolled.
Number of Sites:	Krakow will be the only center participating in this study.
Treatments:	Up to eight (8) pairs of ePTFE cords may be placed in the anterior and/or posterior mitral valve using the Harpoon Medical Device in order to establish effective coaptation of the mitral leaflets.
Endpoints:	
Primary Performance Endpoints: To demonstrate that the Harpoon Medical Device performs as designed and can successfully implant one or more ePTFE artificial cords on either the anterior, posterior, or both leaflets of the mitral valve via a small left thoracotomy on the beating heart and reduce mitral regurgitation from “severe” to less than or equal to “moderate” at the conclusion of the procedure and at 30 days post-procedure.
 
Secondary Performance Endpoints: Severity of mitral regurgitation at 6 months, 12 months and 24 months follow-up shall be tracked and recorded
 
Primary Safety Endpoints: Procedure freedom from Serious Adverse Events (SAEs) during the procedure, at discharge, and at 30 days follow-up shall be tracked and recorded. Rates are expected to be not significantly worse than conventional mitral valve surgery.
 
Secondary Safety Endpoints Freedom from Serious Adverse Events (SAEs) at 6 months, 12 months and 24 months follow-up shall be tracked and recorded

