## SUMMARY OF PRECLINICAL STUDIES

Harpoon has completed enrollment (n = 13) in an Early Feasibility Study across two locations in Poland and has begun enrolling patients in a larger randomized study across multiple countries in Europe to support CE Mark. All thirteen patients enrolled in the EFS had severe degenerative MR and will be evaluated for two years with follow-up visits at 30 days, 6 months, 1 year and 2 years. All echocardiographic studies are graded by an independent core laboratory based on the American Society of Echocardiographer (ASE) Guidelines. An interim report of the Early Feasibility Study based on data available as of December 31, 2015 was published by Gammie et al. in *Circulation* on July 19, 2016. There was 100% procedural success in the thirteen patients enrolled in the EFS and zero procedural and perioperative mortality. Between 3 and 5 chords were implanted in each patient. The average introducer time (the time TAV-5 is inserted into the left ventricle) was 38 minutes and the average skin-to-skin procedure time was 110 minutes. After the ePTFE suture pairs were implanted and secured at the epicardial site; anterior-posterior mitral leaflet coaptation was restored and the severity of MR was significantly reduced. Ten of the EFS patients had None/Trace MR and the balance had Mild MR at the conclusion of the procedure.

As of August 31, 2016, all of the eligible patients in the EFS have completed their thirty day and six month follow-up visits, and 6 patients have completed one-year follow-up. 9 of the 13 patients in the EFS had none/trace or mild MR at six months and 2 were graded as moderate MR and were asymptomatic. The result observed at six months has been stable in each of the six patients who have completed their one-year follow-up visit. Among 6 patients with one-year follow-up, 3 had none/trace MR, 1 had mild, and 2 had moderate MR and were asymptomatic. There has been no mortality, no procedural conversion to open-heart surgery, no stroke, no

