##### Study Hypothesis

Reduction in Mitral Regurgitation from “severe” to less than or equal to “moderate” at the conclusion of the procedure and at 30 days post-procedure.

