##### Endpoints

**Primary Performance Endpoints:** To demonstrate that the Harpoon Medical Device performs as designed and can successfully implant one or more ePTFE artificial cords on either the anterior, posterior, or both leaflets of the mitral valve via a small left thoracotomy on the beating heart and reduce mitral regurgitation from “severe” to less than or equal to “moderate” at the conclusion of the procedure and at 30 days post-procedure.

**Secondary Performance Endpoints:** Severity of mitral regurgitation at 6 months, 12 months and 24 months follow-up shall be tracked and recorded

**Primary Safety Endpoints:** Procedure freedom from Serious Adverse Events (SAEs) during the procedure, at discharge, and at 30 days follow-up shall be tracked and recorded. Rates are expected to be not significantly worse than conventional mitral valve surgery.

**Secondary Safety Endpoints** Freedom from Serious Adverse Events (SAEs) at 6 months, 12 months and 24 months follow-up shall be tracked and recorded

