#### VI. STUDY POPULATION

##### NUMBER OF PATIENTS

Up to 20 patients in PL may be enrolled. The estimated enrollment period is 24 months, and all patients shall be followed for 30 days, 6 months, 12 months and 24 months after implantation in accordance with the Clinical Investigations schedule provided in Section VIII.

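### The primary safety endpoint expects SAE rates not significantly worse than surgery, but a descriptive single-arm study of up to 20 patients with no reference rate, margin or interval cannot support that

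*Combined protocol and SAP*

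**What the plan says.** The primary safety endpoint, given in Section II (Study Summary) and again in Section IV (Endpoints), is freedom from SAEs during the procedure, at discharge and at 30 days. One sentence of expectation follows: "Rates are expected to be not significantly worse than conventional mitral valve surgery". Neither section gives a surgical SAE rate, a margin or a source for one.

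Section V describes a prospective, single-arm, non-randomised early feasibility study. The size is a ceiling: "Up to 20 patients in PL may be enrolled" in Section VI, and "Up to twenty (20) patients in PL will be enrolled" in Section II.

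Section X says the data "are not designed to test a statistical hypothesis, therefore a formal sample size has not been calculated". Results are to be captured by intention to treat and reported descriptively. No confidence interval or other precision statement appears anywhere in the document.

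On the origin of the size, Section X opens with "The sample size for this study was determined from the first early feasibility study for this device". It refers to results at the end of the procedure, "at the time of the hospital dismissal and at one year". The next sentence narrows this to the percentage with MR reduced to moderate or less at the end of the procedure and at 30 days, which are the primary time points.

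**The concern.** The phrase about not being significantly worse sits inside a primary endpoint, and it is the only yardstick given there for judging the SAE results. It can be met in two ways: because the device is about as safe as surgery, or because the sample is too small to show that it is not. At 20 patients or fewer the second route is wide open. With no reference rate, margin or interval, a reader of the final report has nothing to tell the two apart.

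SAEs within 30 days are a realistic prospect. Section III reports two reoperations for delayed tamponade, on post-operative days 5 and 13, among the 13 patients of the first feasibility study. Both appear to meet the SAE definition in Section VIII, since each needed surgical intervention. A small non-zero count here could be reported as satisfying the endpoint when the data cannot exclude a much higher rate.

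**Working it through.** **Inputs from the documents.** Maximum n = 20 (Sections II and VI). First feasibility study: n = 13, with two reoperations for tamponade within 30 days (Section III). Reference rate, margin, alpha, power and interval method: none stated. The plan has no calculation of its own to reproduce.

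**Method.** Exact (Clopper-Pearson) two-sided 95% intervals. For x events in n, the lower limit is the 2.5% quantile of Beta(x, n − x + 1) and the upper limit is the 97.5% quantile of Beta(x + 1, n − x). With zero events the upper limit reduces to 1 − 0.025^(1/n). With n successes in n, the lower limit is 0.025^(1/n).

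**Safety.**
- 0/20: 1 − 0.025^(1/20) = 1 − 0.832 = 16.8%.
- 3/20 (15%): 3.2% to 37.9%. Equivalently, an SAE-free proportion of 17/20 has limits 62.1% to 96.8%.
- Because 20 is a ceiling, these are best-case figures. Zero events allows up to 1 − 0.025^(1/15) = 21.8% at n = 15, and 1 − 0.025^(1/10) = 30.8% at n = 10.
- An event type with a true rate of 5% appears at least once in 20 patients with probability 1 − 0.95^20 = 64%, so it is missed altogether in about 36% of such studies.

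Three events is a plausible count. The two tamponade reoperations give 2/13 = 15.4% (exact interval about 2% to 45%), and 20 × 2/13 = 3.1.

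**What not significantly worse would mean at 3/20.** Treat the surgical rate as a known constant and test one-sided at 2.5%, matching the lower limit of the two-sided 95% interval; both are assumptions, since the plan fixes neither. The lower limit of 3.2% means that 3/20 is not significantly above any reference rate of about 3.2% or more. The same data are compatible with a true rate of 37.9%. Zero events cannot be significantly above any reference rate, whatever the sample size.

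**Performance.**
- 20/20 with MR at most moderate: lower limit 0.025^(1/20) = 83.2%.
- 18/20: 68.3% to 98.8%.

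**Basis of the size.** Section X names no rate, target or rule. A search over exact single-arm binomial designs used assumed success rates of 11/13, 0.90, 0.95 and 0.99, null rates of 0.50 to 0.80, one-sided alpha of 0.025 or 0.05, and power of 80% or 90%. The first qualifying n ranged from 5 to 183; for 11/13 against 0.80, none below 200 qualified. Some combinations land on 20 (0.65 against 0.90, alpha 0.05, power 80%), but only because the assumptions can be chosen to do so. The search neither confirms nor refutes a link to the first study.

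Section III does not report the first study's MR percentage at 30 days or at dismissal. At its cut-off, "6 patients have completed one-year follow-up". The results printed in the protocol therefore do not cover all the time points that Section X cites.

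**The case against.** The strongest reply is that the plan already disclaims inference. The endpoint text says SAEs will be recorded, and that rates are expected to compare acceptably; it schedules no test against surgery. Section X says no statistical hypothesis is tested. A descriptive early feasibility study needs no power calculation, and descriptive reporting does not rule out intervals. All of this stands. A reader might infer that a formal comparison with surgery is planned, or that the study is undersized for one; the documents support neither reading. What the reply leaves unanswered is why a primary endpoint uses the language of significance at all, with nothing to measure it against.

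A reader might also take Section X to contradict itself, and conclude that the stated basis for the size is untrue. That does not follow. The text denies only a formal calculation, and an earlier study can inform a size without one. Nothing in the documents shows that the first study was not used. Nor is it fair to say that the basis ignores the primary time points, since the second sentence names exactly those. Dismissal and one year are additions in the general sentence.

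The heading "Study Hypothesis" in Section IV might likewise suggest a planned test. The text beneath it is a clinical expectation with no null value or threshold, so renaming it is a matter of editorial taste.

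**Conclusion.** The point holds for the comparative safety wording and the missing intervals. As written, the safety expectation could be declared met through imprecision alone: at the full 20 patients, an SAE-free result still allows a true rate up to 16.8%, and three patients with SAEs allows up to 37.9%. Smaller enrolment widens these limits. The figures assume that each patient counts once, that outcomes are independent, and that all enrolled patients contribute to the 30-day denominator. The last is optimistic, because Section VII ends data collection at discharge for patients in whom the device was not used.

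The basis of the size is a secondary wording point: it is unexplained and cannot be reproduced, and no more than that is shown. The size itself is not at fault for a descriptive feasibility study.

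**What to change.** 1. In Sections II and IV, replace the sentence on rates relative to conventional surgery with one such as: *SAE rates will be described; no comparative or non-inferiority conclusion against surgery will be drawn from this study.*
2. In Section X, state that the primary performance proportions (end of procedure and 30 days) and the 30-day SAE-free proportion will be reported with exact two-sided 95% intervals, and name the denominator for each.
3. In Section X, give the expected precision for up to 20 patients, using the 0/20, 3/20, 18/20 and 20/20 limits above and the zero-event limits at 15 and 10.
4. Name the first-study result relied on for the size and how it led to a ceiling of 20, with time points matching the primary endpoint; if there was no such result, delete the sentence. The sponsor should not be asked to state that the size was not derived from the first study, since the documents do not show that.

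The cost is wording in three sections and a few interval calculations, with no extra patients, visits or tests. The stated safety claim becomes less favourable, which is the real price.

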## **XI. STUDY ORGANISATION**

### **INVESTIGATIONAL SITE PERSONNEL**

#### **Investigator and co-investigators**

The Investigator is responsible for ensuring that this study is conducted according to this protocol and that signed Informed Consent is obtained from each patient prior to their inclusion in this study.

It is the Investigator's responsibility to ensure that all staff assisting with this study have the appropriate qualifications and are fully instructed on the study procedures and respect patient confidentiality, as specified in the Investigator Agreement with the Sponsor.

The Investigator is responsible for ensuring that the conduct of the study conforms to the EC and Competent Authority (CA) requirements and provides all necessary communication with the EC, but not limited to, annual study reports and required adverse event notifications.

Specific responsibilities:

- An Investigator shall conduct an investigation in accordance with the ethical principles that have their origin in the Declaration of Helsinki, the ISO14155:2011, the signed Investigator Agreement with the Sponsor, the Protocol, applicable national regulations, and any conditions of approval imposed by a local regulatory body, Ethical Committee (EC), or Competent Authority.
- The standardized Case Report Forms (CRFs) will be used to collect complete and accurate records of the clinical data from the study. The Investigator is responsible for collecting and accurately recording the data generated for this study.
- Investigators will maintain a screening log that will record the date of informed consent, the date of screening, the enrollment status (enrolled/excluded) and the reason for exclusion for all screen failures.
- A participating Investigator shall maintain accurate, complete, and current records (listed in detail in the Investigator Agreement) relating to the Investigator's participation in the study for a period of 10 years or longer, as may be required by applicable laws, rules and regulations.
- An Investigator shall prepare and submit complete, accurate, and timely reports on adverse events, withdrawal of EC approval, progress, deviations from the protocol, informed consent,

termination or completion of the study, and other study-related aspects requested by the EC. (These are described in more detail in the Investigator Agreement.)

### Study Coordinator

Each site in this study is required to identify a Study Coordinator who will be responsible for, but not limited to, the following:

- Scheduling diagnostic and assessment procedures.
- Informing all study team members of scheduled treatments.
- Paging study team members on the morning of scheduled treatments to ensure that all necessary personnel will be present.
- Entering all study data into the Case Report Forms.
- Maintaining a list of all patients screened for the study and those who have entered the study and their patient numbers.
- Maintaining the Device Accountability Log.
- Scheduling all follow-up visits within the appropriate follow-up windows and ensuring that all follow-up data is collected in accordance with the protocol.

### CLINICAL MONITORING

The clinical study site(s) shall be monitored in accordance with policies at Harpoon Medical, Inc. and those federal regulations that pertain to clinical research; namely ISO14155:2011.

A monitoring plan will be developed prior to the initiation of the investigation which outlines the extent and nature of monitoring appropriate for the clinical investigation, including the frequency of visits, the strategy for source data verification, based on considerations such as the objective, design, complexity, size, critical data points and endpoints of the clinical investigation.

The Sponsor or its designated representative, qualified by training and experience, will be responsible for monitoring and overseeing the conduct of the study. These responsibilities include maintaining regular contact with each Investigational site and conducting on-site monitoring visits at the Investigational site to ensure compliance with this Protocol, to verify that accurate and complete data are being submitted in a timely manner, and to verify that the Investigational site facilities continue to be adequate.

Monitors are responsible for assuring that each Investigator and his/her staff clearly understand and accept their obligations under the clinical investigation through site visits, written communications and phone calls between the Monitor and the PI and staff.

During the course of the investigation, the Monitor shall assure that the PI and his/her staff:

- Understand and agree to the requirements of the protocol;
- Agree to their obligations to conduct the study;
- Accept the obligation to obtain informed consent using the approved Patient Information Sheet;
- Have access to an adequate number of suitable patients to conduct the investigation;

- Have facilities adequate to conduct the clinical investigation; and
- Have sufficient time to fulfill his/her obligations under the study;

During the course of a clinical investigation, the Monitor shall periodically visit the clinical investigation site to assure that:

- Changes to the protocol have been submitted and approved by ethics committees;
- Adverse events (anticipated and unanticipated) are recorded and reported in accordance with the spirit of Good Clinical Practices (GCPs), ISO-14155-2011, Declaration of Helsinki, and as per the Investigator Agreement;
- Accurate, complete, and current records are being maintained;
- Patient confidentiality of records and study participation are being maintained; and
- Accurate, complete and timely reports are being made to Sponsor and to the EC.

Patient information shall remain confidential. Should any new knowledge about the patients' medical condition become known, it will be kept confidential. Any data that may be published in scientific journals will not reveal the identity of the patients. Data retrieved (case report forms, surgery reports, discharge summaries, laboratory and test reports, etc.) from the site will identify patients by their patient number / patient name code only.

## CLINICAL EVENTS COMMITTEE

The purpose of the Clinical Events Committee (CEC) will be to review specific information obtained from research patients who are participating in the study. The CEC will have the authority to undertake a critical examination of this information and to draw conclusions regarding pre-specified events that may or may not correspond with the conclusions of the investigator or Harpoon Medical for a specific site. Should a discrepancy arise the CEC's conclusion will serve as the final decision for publication.

The CEC will draw its own conclusions as to whether or not certain clinical events occurred as a result of the patient's study participation. Definitions of clinical endpoints are previously established and are recorded in the Clinical Investigation Plan for use by the committee members. The CEC has the authority to request all available data for a given patient and to use state-of-the-art scientific, technical and clinical information in order to reach its conclusions. These conclusions are required to be drawn independently from those of the treating physician, investigator and Harpoon Medical.

The CEC is composed of 3 physicians: 2 Interventional Cardiologists and a Cardiac Surgeon in clinical practice. These physicians should:

- Not participate in the clinical study
- Have no conflict of interest regarding the device under evaluation
- Be independent from the clinical sites

